6.5.7.3 Primary Efficacy Analyses

The primary comparisons in this trial will be between NOV03 versus saline at Day 57 in the FAS with available data per subject using the following estimands

- Endpoint:
 - CFB in tCFS in the study eye at Day 57
 - CFB of Dryness Score (VAS) at Day 57
- Intercurrent event:
 - Discontinuation of study medications is ignored. [treatment policy strategy]
 - Non-optimal compliance is ignored. [treatment policy strategy]
 - Withdrawal due to any reason. Missing data not imputed. [hypothetical strategy if overall study discontinuation rate is <5%]
- Population-level summary:
 - Difference in the mean CFB in tCFS in the study eye at Day 57 between NOV03 and saline
 - Difference in the mean CFB of Dryness Score (VAS) at Day 57 between NOV03 and saline

If the overall study discontinuation rate in the FAS is $\geq 5\%$ then the primary analysis will be based on imputation methodology using the following estimands:

- Endpoint:
 - CFB in tCFS in the study eye at Day 57
 - CFB of Dryness Score (VAS scale) at Day 57
- Intercurrent event:
 - Discontinuation of study medications is ignored. [treatment policy strategy]
 - Non-optimal compliance is ignored. [treatment policy strategy]
 - Withdrawal due to lack of efficacy or adverse events: baseline observation carried forward (BOCF) is used to impute missing data [hypothetical strategy if overall study discontinuation rate $\geq 5\%$]
 - Missing data without withdrawal or withdrawal due to reasons other than lack of efficacy or adverse events: multiple imputations using randomized treatment-based Markov Chain Monte Carlo (MCMC) is used to impute missing data [hypothetical strategy if overall study discontinuation rate $\geq 5\%$]
- Population-level summary:
 - Difference in the mean CFB in tCFS in the study eye at Day 57 between NOV03 and saline
 - Difference in the mean CFB of Dryness Score (VAS scale) at Day 57 between NOV03 and saline

The primary comparison in this trial will be between NOV03 versus saline at Day 57. The primary efficacy endpoints (e.g. CFB in total corneal fluorescein staining [NEI scale] and Dryness Score) will be tested using hierarchical fixed sequence testing and summarized descriptively (n, mean, standard deviation, median, min, and max) and analyzed separately using an ANCOVA model with terms for baseline value, and treatment.

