**6.5.7.6 Sensitivity Analyses****6.5.7.6.1 Sensitivity Analyses for Primary Efficacy Endpoints**

Two-sample t-tests (equal variance assumed), Wilcoxon rank sum tests and mixed-effect repeated measures analysis comparing treatment groups will be performed as sensitivity analyses. The mixed-effect repeated measures model will include treatment, baseline value, visit, and the interaction between treatment and visit as fixed effects, and subject as a random effect. An unstructured covariance matrix will initially be used to model the covariance among repeated measures; however, if the model fails to converge using this covariance structure, either heterogeneous TOEPLITZ, homogeneous TOEPLITZ, or compound symmetry will be implemented according to the Akaike information criterion with a correction for finite sample sizes (AICc).

Sample SAS two-sample t-test code:

```
PROC TTEST DATA=INDATA;
  CLASS <TREATMENT>;
  VAR <ENDPOINT>;
RUN;
```

Sample SAS Wilcoxon rank sum test code:

```
PROC NPAR1WAY DATA=INDATA WILCOXON;
  CLASS <TREATMENT>;
  VAR <ENDPOINT>;
RUN;
```

Sample SAS mixed-effect repeated measures analysis code:

```
PROC MIXED DATA=INDATA;
  CLASS <TREATMENT> <VISIT>;
  MODEL <ENDPOINT>=<TREATMENT> <VISIT> <TREATMENT>*<VISIT> <BASELINE>;
  REPEATED <VISIT> / SUBJECT=<SUBJECT> TYPE=UN;
  RANDOM <SUBJECT>;
```

```
ESTIMATE 'NOV03-SALINE' <TREATMENT> -1 1 / ALPHA=0.05 CL;  
RUN;
```

Where 'Saline' is <TREATMENT>=0 and 'NOV03' is <TREATMENT>=1.

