6.5.7.6.2 Sensitivity Analyses for Secondary Efficacy Endpoints

For quantitative secondary efficacy endpoints, two-sample t-tests, Wilcoxon rank sum tests and mixed-effect repeated measures analysis comparing treatment groups will be performed as sensitivity analyses.

The mixed-effect repeated measures model will include treatment, baseline value, visit, and the interaction between treatment and visit as fixed effects, and subject as a random effect. An unstructured covariance matrix will initially be used to model the covariance among repeated measures; however, if the model fails to converge using this covariance structure, either heterogeneous TOEPLITZ, homogeneous TOEPLITZ, or compound symmetry will be implemented according to the AICc.

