6.5.7.6.3 Sensitivity Analyses for Other Pre-specified Efficacy Endpoints

For quantitative efficacy variables, two-sample t-tests, Wilcoxon rank sum tests and mixed-effect repeated measures analysis will be presented as sensitivity analyses.

For qualitative efficacy variables, Pearson chi-squared analysis comparing the treatment groups will be performed as sensitivity analyses.

Sample Pearson chi-squared analysis code:

```
PROC FREQ DATA=INDATA;  
  TABLES <TREATMENT>*<ENDPOINT> / CHISQ;  
RUN;
```

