7 INDEX OF PLANNED TABLES, FIGURES, AND LISTINGS

Tables

Number	Title
14.1.1.1	Overall Disposition and Subject Accountability – FAS
14.1.1.2	Overall Disposition and Subject Accountability – PPS
14.1.1.3	Overall Disposition and Subject Accountability – SAF
14.1.2.1	Overview of Analysis Sets – Randomized Subjects
14.1.2.2	Reasons for Exclusion from Study Populations – Randomized Subjects
14.1.3	Major Protocol Deviations – FAS
14.1.4.1	Demographic and Baseline Characteristics – FAS
14.1.4.2	Demographic and Baseline Characteristics – PPS
14.1.4.3	Demographic and Baseline Characteristics – SAF
14.1.5.1	Baseline Ocular Characteristics – FAS
14.1.5.2	Baseline Ocular Characteristics – PPS
14.1.5.3	Baseline Ocular Characteristics – SAF
14.1.6.1	Study Eye Ocular Medical History – FAS
14.1.6.2	Fellow Eye Ocular Medical History – FAS
14.1.6.3	Subject Level Ocular Medical History – FAS
14.1.6.4	Non-ocular Medical History – FAS

- 14.1.7.1 Study Eye Ocular Concomitant Medications – FAS
- 14.1.7.2 Fellow Eye Ocular Concomitant Medications – FAS
- 14.1.7.3 Subject Level Ocular Concomitant Medications – FAS
- 14.1.7.4 Non-ocular Concomitant Medications – FAS
- 14.1.8 Study Medication Exposure and Compliance – SAF
- 14.2.1.1 Analyses of Change from Baseline tCFS and Dryness Score (VAS) at Day 57 – FAS
- 14.2.1.2 Analyses of Change from Baseline tCFS and Dryness Score (VAS) at Day 57 – PPS
- 14.2.2 Robustness Analyses of Change from Baseline tCFS and Dryness Score (VAS) at Day 57 (Discontinuation Rate $\geq 5\%$) – FAS
- 14.2.3 Sensitivity Analyses of Change from Baseline tCFS and Dryness Score (VAS) at Day 57 – FAS
- 14.2.4.1 Analyses of Secondary Efficacy Endpoints – FAS
- 14.2.4.2 Sensitivity Analyses of Secondary Efficacy Endpoints – FAS
- 14.2.5.1 Analysis of Dryness Score (VAS) – FAS
- 14.2.5.2 Sensitivity Analysis of Dryness Score (VAS) – FAS
- 14.2.6.1 Analysis of Study Eye tCFS – FAS
- 14.2.6.2 Analysis of Fellow Eye tCFS – FAS
- 14.2.6.3 Sensitivity Analysis of Study Eye tCFS – FAS
- 14.2.6.4 Sensitivity Analysis of Fellow Eye tCFS – FAS
- 14.2.7.1 Analysis of Study Eye Central Sub-region CFS (NEI scale) – FAS
- 14.2.7.2 Analysis of Fellow Eye Central Sub-region CFS (NEI scale) – FAS
- 14.2.7.3 Sensitivity Analysis of Study Eye Central Sub-region CFS (NEI scale) – FAS
- 14.2.7.4 Sensitivity Analysis of Fellow Eye Central Sub-region CFS (NEI scale) – FAS
- 14.2.7.5 Analysis of Study Eye Inferior Sub-region CFS (NEI scale) – FAS

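### The sample MMRM code asks for a treatment main effect, not the Day 57 difference, and its subject random effect is redundant and mis-declared

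*SAP*

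**What the plan says.** SAP 6.5.7.6.1 supports the two primary ANCOVAs with t-tests, Wilcoxon tests and a mixed-effect repeated measures model. The fixed effects are treatment, baseline, visit and treatment-by-visit. Subject is a random effect, and the repeated covariance is unstructured at first. If that fails to converge, "either heterogeneous TOEPLITZ, homogeneous TOEPLITZ, or compound symmetry will be implemented according to the Akaike information criterion", in its small-sample form. Protocol 10.4.5 and SAP 6.5.7.6.2 describe the same model, the latter with "the interaction between treatment and visit as fixed effects, and subject as a random effect".

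The sample code declares "CLASS <TREATMENT> <VISIT>", uses an unstructured `REPEATED` statement by subject, adds "RANDOM <SUBJECT>", and requests one comparison: "ESTIMATE 'NOV03-SALINE' <TREATMENT> -1 1 / ALPHA=0.05 CL". It has no `LSMEANS` statement and no visit-specific contrast.

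The time point of interest is stated elsewhere. SAP 6.5.7.3 says "The primary comparison in this trial will be between NOV03 versus saline at Day 57". In SAP section 7, Table 14.2.3 is titled "Sensitivity Analyses of Change from Baseline tCFS and Dryness Score (VAS) at Day 57". For the other pre-specified endpoints, SAP 6.5.7.6.3 says that "mixed-effect repeated measures analysis will be presented as sensitivity analyses", again without a contrast.

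**The concern.** When a model contains treatment-by-visit, the treatment difference at a given visit is the treatment term plus that visit's interaction term. A contrast on the treatment term alone does not pick out Day 57. A programmer who follows the sample code would put something other than a Day 57 estimate under a Day 57 title, and that row could not show whether the Day 57 ANCOVA is robust.

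The gap can spread. The secondary endpoints need Day 15 and Day 57 results and the other endpoints need results at each visit, yet 6.5.7.6.2 and 6.5.7.6.3 give no contrast of their own. If the template is reused, tCFS gets one number for all three days.

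The random effect raises two further points. In the prose it duplicates what the unstructured matrix already covers. In the code it is not the subject intercept that the prose describes, because the subject variable is missing from the class list.

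**Working it through.** **Inputs from the documents.** Post-baseline visits at Day 15, 29 and 57 (schedule of assessments). From SAP 6.5.10: 250 per arm, two-sided alpha 0.05, tCFS difference -1.0 with SD 2.8, Dryness difference -10 with SD 28, stated power 97.9% each. Coding saline = 0, NOV03 = 1, so the sign of the contrast is right.

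**The plan's own figure.** SE at Day 57 = 2.8 × √(2/250) = 0.2504. z = 1.0/0.2504 = 3.99. Power = Φ(3.99 - 1.96) = 97.9%. Dryness has the same ratio (SE 2.504, z 3.99). The stated power reproduces and is not in dispute.

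**Contrast.** Write the treatment effects as τ0, τ1 and the interactions as γ0v, γ1v. The difference at visit v is (τ1 - τ0) + (γ1v - γ0v).

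- Add a constant c to τ1 and subtract c from γ1v at all three visits. Every cell mean is unchanged, but τ1 - τ0 moves by c. So τ1 - τ0 alone is not estimable. A rank check agrees: the over-parameterised design has 13 columns and rank 7, and the treatment-only contrast lies outside its row space.
- With interaction coefficients of -1/3 (saline) and +1/3 (NOV03) at each visit, the contrast is estimable and equals (d15 + d29 + d57)/3.
- With interaction coefficients of -1 and +1 at Day 57 only, it is estimable and equals d57. The code does not request this.

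**Size (illustration).** The documents give no Day 15 or Day 29 effects and no between-visit correlation. I assume complete data on 250 per arm, SD 2.8 at each visit, a common correlation ρ and the averaged contrast. Then SE of the average = 0.2504 × √((1 + 2ρ)/3), which is 0.183, 0.204, 0.224 and 0.242 for ρ = 0.3, 0.5, 0.7 and 0.9. The chance of a significant result favouring NOV03 is Φ(|mean|/SE - 1.96).

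| tCFS effect at Day 15 / 29 / 57 | Reported mean | Significant, ρ = 0.5 to 0.7 | Day 57 contrast |
|---|---|---|---|
| -1.0 / -1.0 / -1.0 | -1.00 | 99.8% to 99.4% | -1.0, 97.9% |
| -0.75 / -0.9 / -1.0 | -0.88 | 99% to 98% | -1.0, 97.9% |
| -0.5 / -0.75 / -1.0 | -0.75 | 96% to 92% | -1.0, 97.9% |
| -0.3 / -0.6 / -1.0 | -0.63 | 87% to 81% | -1.0, 97.9% |
| -1.0 / -0.5 / 0 | -0.50 | 69% to 61% | 0, 2.5% |

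Over ρ = 0.3 to 0.9 the fourth row runs from 93% to 75% and the last from 78% to 54%. For Dryness, -3 / -6 / -10 would be reported as (-3 - 6 - 10)/3 = -6.3 instead of -10.

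**Random effect in the prose.** A random intercept adds one variance to every cell of the 3 × 3 covariance matrix.

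| Structure | Parameters with random intercept | Rank |
|---|---|---|
| Unstructured | 6 + 1 = 7 | 6 |
| Homogeneous Toeplitz | 3 + 1 = 4 | 3 |
| Compound symmetry | 2 + 1 = 3 | 2 |
| Heterogeneous Toeplitz | 5 + 1 = 6 | 6 |

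The term is redundant in the first three. With heterogeneous Toeplitz it is identified, but it uses as many parameters as the unstructured matrix alone, so that fallback no longer simplifies anything.

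**Random effect in the code.** Subject is not in the class list, so a numeric ID enters as a continuous variable with one random coefficient, not as an intercept per subject. A character ID would give an error. This rests on general software behaviour and on how the ID is stored, which the documents do not state. The estimability and rank results do not depend on it.

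**The case against.** The code is labelled as a sample, serves a sensitivity analysis and feeds no decision rule. The t-test, Wilcoxon, per-protocol, LOCF and multiple-imputation analyses remain. All of that is right and limits the weight of the point.

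The intended visit can also be inferred: the section covers the primary endpoints, which are defined at Day 57, and the table title says so. That is fair, but it shows that the code departs from the intention. The model description itself names no visit, so nothing there overrides the code.

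The effect profiles are chosen, not derived. A Day 15 effect of -0.3 has z = 0.3/0.2504 = 1.2 and power of about 22%, which sits poorly with a plan that tests the Day 15 endpoints first among the secondaries. This stands as a caution on size: the milder rows of the table may be nearer the sponsor's expectation, and a constant effect gives no error in the estimate. The fading profile departs from the design assumption, and no efficacy claim would follow from it, since the Day 57 ANCOVA would favour NOV03 in only 2.5% of such trials.

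Finally, the redundant random effect leaves the marginal model under the unstructured matrix unchanged. A convergence problem that triggers the fallback needlessly is possible but has not been shown. A character ID would stop the program rather than give a wrong answer. Neither point removes the need to correct the specification.

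**Conclusion.** The concern holds. As coded, the MMRM comparison is either not estimable or the average of three visit differences. It matches the Day 57 difference only if the three differences happen to average to that value, as with a constant effect. How far it would miss cannot be determined from the documents. Under the assumptions above, the reported tCFS effect is between 63% and 100% of a Day 57 value of -1.0 when the effect builds up or stays constant, and -0.5 when the effect has faded to zero.

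The subject random effect is redundant under three of the four covariance structures named, and the code does not fit the term that the prose describes. The trial's conclusion does not rest on this analysis. It should still be corrected before unmasking, so that the choice of contrast is not made after the data are seen.

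**What to change.** - In SAP 6.5.7.6.1, replace the `ESTIMATE` line with visit-specific differences from `LSMEANS <TREATMENT>*<VISIT>`, reporting NOV03 minus saline with its 95% confidence interval.
- In SAP 6.5.7.6.1 to 6.5.7.6.3, state the visit: Day 57 for Day 57 endpoints, Day 15 for the Day 15 secondary endpoints, Day 29 and each measured visit for the other endpoints.
- Add the subject variable to the `CLASS` statement.
- Delete the `RANDOM` statement, and remove the subject random effect from protocol 10.4.5 and SAP 6.5.7.6.1 and 6.5.7.6.2, for the fallback structures as well as the unstructured matrix.

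The cost is a few lines of sample code and about one sentence in each section. The protocol wording needs the same edit; if only the SAP is changed, SAP 6.6, which now lists no changes to the planned analyses, should record the difference. No data collection or patient procedure is affected.

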6.5.7.6.2 Sensitivity Analyses for Secondary Efficacy Endpoints

For quantitative secondary efficacy endpoints, two-sample t-tests, Wilcoxon rank sum tests and mixed-effect repeated measures analysis comparing treatment groups will be performed as sensitivity analyses.

The mixed-effect repeated measures model will include treatment, baseline value, visit, and the interaction between treatment and visit as fixed effects, and subject as a random effect. An unstructured covariance matrix will initially be used to model the covariance among repeated measures; however, if the model fails to converge using this covariance structure, either heterogeneous TOEPLITZ, homogeneous TOEPLITZ, or compound symmetry will be implemented according to the AICc.

6.5.7.6.3 Sensitivity Analyses for Other Pre-specified Efficacy Endpoints

For quantitative efficacy variables, two-sample t-tests, Wilcoxon rank sum tests and mixed-effect repeated measures analysis will be presented as sensitivity analyses.

For qualitative efficacy variables, Pearson chi-squared analysis comparing the treatment groups will be performed as sensitivity analyses.

Sample Pearson chi-squared analysis code:

```
PROC FREQ DATA=INDATA;  
  TABLES <TREATMENT>*<ENDPOINT> / CHISQ;  
RUN;
```

6.5.8 Statistical/Analytical Issues

6.5.8.1 Study Days

Study Day 1 will be defined as the date of Visit 1/Day 1. For events before the Day 1 visit, the study day will be calculated as the difference in day between the Day 1 visit and the date of interest. Thus, the day prior to the Day 1 visit will be defined as Day -1.

6.5.8.2 Analysis Visits

The eCRF nominal study visits will be used for analysis. For subjects who withdraw from the study, if they withdraw at a regular scheduled visit, the data collected at the time of withdrawal will be summarized under the regular visit; if they withdraw between scheduled visits, the early termination visit will be treated as an unscheduled visit. For the purposes of table summarization, the first visit for each nominal study visit will be used.

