6.5.9.4 Other Safety Measurements

Visual acuity, slit-lamp biomicroscopy, dilated fundoscopy, and intraocular pressure will be summarized by treatment group and visit using descriptive statistics in SAF. Changes from baseline will also be summarized where appropriate. For assessments performed by eye, study eye and fellow eye will be summarized separately.

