6.5.9.4.3 Dilated Fundoscopy Examination

A dilated fundoscopy examination will be performed during the trial at screening, Visit 4 and early termination. Observations will be graded as Normal, Abnormal CS or Abnormal NCS. Vitreous, retina, macula, choroid and optic nerve will be examined. If 'Check if no changes since Visit 0' is checked, the results of the tests at Visit 0 will be used for analysis at that timepoint. Listings will display 'No changes since Visit 0'. Descriptive statistics for the grading by each domain will be presented for study eye and fellow eye by treatment and overall at baseline and all post-baseline visits in the SAF. Shifts from baseline indicative of worsening will also be summarized. Worsening is defined as a shift from normal to abnormal not clinically significant, normal to abnormal clinically significant, and abnormal not clinically significant to abnormal clinically significant.

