6.5.9.4.4 Intraocular Pressure

Intraocular pressure (IOP) will be measured in each eye by contact tonometry by the examiner and the results will be recorded in mmHg at screening, Visit 4 and early termination. A single measurement will be made to obtain a determination of IOP. Descriptive statistics for the IOP measurement will be presented for study eye and fellow eye by treatment and overall at baseline and all post-baseline visits in the SAF. Changes from baseline will also be summarized.

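### Early-termination examinations made between scheduled visits have no row in the by-visit safety tables, so a withdrawing subject's only post-baseline intraocular pressure and fundoscopy can go untabulated

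*SAP*

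**What the plan says.** SAP 6.5.8.2 sets the visit basis for analysis: "The eCRF nominal study visits will be used for analysis". It then gives two rules for subjects who withdraw:

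- Leaving at a visit: "if they withdraw at a regular scheduled visit, the data collected at the time of withdrawal will be summarized under the regular visit".
- Leaving between visits: "if they withdraw between scheduled visits, the early termination visit will be treated as an unscheduled visit".

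It closes with the rule for tables: "For the purposes of table summarization, the first visit for each nominal study visit will be used". SAP 6.5.8.6 refers back to this section for withdrawals, and there is no separate visit rule for safety data.

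SAP 6.5.9.4 says that visual acuity, slit lamp, fundoscopy and IOP "will be summarized by treatment group and visit using descriptive statistics in SAF". On timing, SAP 6.5.9.4.3 states: "A dilated fundoscopy examination will be performed during the trial at screening, Visit 4 and early termination". SAP 6.5.9.4.4 says of IOP that "the results will be recorded in mmHg at screening, Visit 4 and early termination". Both subsections promise summaries at baseline and every post-baseline visit in the safety set.

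The protocol (4.3, Early Termination, and 8.4.2) asks a subject who leaves early to undergo the full set of Visit 4 evaluations.

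**The concern.** The protocol asks for a full examination when a subject leaves, and the SAP then gives that examination no place in the by-visit tables if it falls between visits. For IOP and fundoscopy there is normally no earlier post-baseline value to fall back on. The subjects concerned are selected by withdrawal, which can be related to how the eye is doing.

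Safety and tolerability are the trial's secondary objective (Protocol 3.2), and SAP 5.2 lists these examinations among the means of assessing them. At stake is whether the IOP and fundoscopy tables describe everyone who was examined after dosing, or only those who reached a scheduled visit. The two parts of the SAP also cannot both be programmed as written: 6.5.9.4.3 and 6.5.9.4.4 count early termination as a time point, and 6.5.8.2 takes it out of the nominal visits.

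**Working it through.** **Step 1. What is collected, and when.** Protocol Appendix 1 and SAP Table 1 agree. Visual acuity and slit lamp are done at Visits 0, 1, 2, 3 and 4/early termination (ET). IOP and fundoscopy are done at Visit 0 and Visit 4/ET only.

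**Step 2. Where each result goes under SAP 6.5.8.2.** This assumes that scheduled visits before withdrawal were attended.

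| Subject leaves | IOP and fundoscopy at ET | Visual acuity and slit lamp |
|---|---|---|
| At Visit 2 or 3 | Tabulated under that visit | Tabulated |
| Before Visit 2 | No nominal row; no other scheduled post-baseline value | ET value has no row; no other scheduled post-baseline value |
| Between Visits 2 and 3 | No nominal row; no other scheduled post-baseline value | Visit 2 tabulated; ET value has no row |
| Between Visits 3 and 4 | No nominal row; no other scheduled post-baseline value | Visits 2 and 3 tabulated; ET value has no row |
| Without an ET examination | Nothing collected, so the gap is not due to this rule | Earlier visits tabulated |

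**Step 3. The planned outputs (SAP section 7).** Tables 14.4.1, 14.4.2, 14.4.4 and 14.4.6 are laid out by visit. No table is indexed for ET or unscheduled visits. Those records appear in Listings 16.2.9.1 to 16.2.9.4 and 16.3.1. The worsening-shift Tables 14.4.3 and 14.4.5 are not titled by visit, so their handling of unscheduled records is not defined.

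**Step 4. How many subjects.** The plan's discontinuation allowance comes first (Protocol 10.3, SAP 6.5.10): 250 / (1 − 0.10) = 277.8, so 278 per arm against 280 planned. That is consistent. Expected withdrawals are 560 × 0.10 = 56, or 28 per arm.

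The number with an untabulated ET examination is

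560 × d × s × q,

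where d is the discontinuation rate, s the share of withdrawals that fall between visits, and q the share of those who attend an ET examination. The documents give d = 0.10 as an assumption. They give neither s nor q.

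| s (with d = 0.10, q = 1) | Subjects | Share of 560 |
|---|---|---|
| 0 | 0 | 0% |
| 0.25 | 14 | 2.5% |
| 0.50 | 28 | 5.0% |
| 0.75 | 42 | 7.5% |
| 1 | 56 | 10.0% |

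With s = 0.5 and q = 0.5 the count is 560 × 0.10 × 0.5 × 0.5 = 14. At a discontinuation rate of 5%, the point below which the SAP keeps the available-data primary analysis, the maximum is 560 × 0.05 = 28.

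One illustration for s, assumed and not documented: withdrawal spread evenly over Days 2 to 54. The Visit 2 window (Days 14–16) covers 3 days and the Visit 3 window (Days 27–31) covers 5, so 53 − 8 = 45 days lie between visits. Then s = 45/53 = 0.849, and 56 × 0.849 = 47.5, about 48 subjects (8.5% of 560). Clustering of withdrawals at visits would lower this.

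**The case against.** The strongest reply has five parts.

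1. **Important findings are still counted.** Protocol 9.1 makes a logMAR worsening of 0.22 or more from Visit 0 an adverse event, and its general definition covers unfavourable signs seen by the physician. Treatment-emergent events are tabulated by subject and eye without regard to nominal visit (SAP 6.5.9.1.7). This stands. A reader might infer that a bad ET finding would surface only in a listing; the documents do not support that. The backstop is partial, however. In the sections available there is no numerical adverse-event rule for IOP or fundoscopy, and the shift definition includes moves to abnormal but not clinically significant, which need not be an adverse event.

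2. **Exclusion is inferred.** No sentence says that unscheduled records are kept out of tables. This is true, but 6.5.8.2 gives a between-visit ET examination no nominal visit, and the by-visit tables have no other row. The inference is strong for those tables. It does not extend to the shift tables, which are simply left open.

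3. **Many subjects are untouched.** Those who stop treatment are encouraged to attend all later visits (Protocol 8.4.2), those who leave at a visit are tabulated there, and some who are lost have no ET examination. All of this stands. A reader might infer that most early withdrawals lose their values, but withdrawal timing is not documented.

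4. **The direction of any distortion is unknown.** A reader might infer that the tables lean towards no difference between arms. That would require knowing which arm loses which findings, and the plan gives no basis for it. The safety comparison is descriptive, with no test.

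5. **Visual acuity and slit lamp are mostly covered** by Visits 2 and 3. This stands, except for the ET value itself and for subjects who leave before Visit 2.

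**Conclusion.** The point holds in a limited form. Followed as written, SAP 6.5.8.2 can remove from Tables 14.4.4 and 14.4.6 the only post-baseline fundoscopy and IOP of subjects who withdraw between visits and attend an ET examination. This conflicts with 6.5.9.4.3 and 6.5.9.4.4. The effect on Tables 14.4.1 and 14.4.2 is smaller.

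The size is 0 to 56 of 560 subjects at the assumed 10% discontinuation; it cannot be narrowed without the timing of withdrawals and attendance at ET examinations. The loss is of measured values and grades in tables. It is not a loss of adverse-event counts or of the data themselves. The conclusion rests on reading the by-visit tables as containing nominal visits only. It does not touch the efficacy analyses, and it is a modest point that is cheap to put right.

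**What to change.** - **SAP 6.5.8.2:** keep the nominal-visit rule for efficacy. Add that safety examinations follow 6.5.9.4, so that 6.5.8.2 agrees with 6.5.9.4.3 and 6.5.9.4.4.
- **SAP 6.5.9.4 and Tables 14.4.1, 14.4.2, 14.4.4 and 14.4.6:** add a row for early termination / last post-baseline value that includes ET and unscheduled records, with the number of eyes per arm.
- **Tables 14.4.3 and 14.4.5:** state that worsening shifts include ET and unscheduled records.
- **Optional:** a count of eyes that reach the 0.22 logMAR worsening threshold. It is not needed to close the gap, because Protocol 9.1 already makes such a loss an adverse event.

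The cost is a SAP amendment before database lock and unmasking, for which SAP section 4 already provides, and a few extra table rows. No new data, visits or subjects are needed. The last-value row mixes different lengths of exposure, so it should stand beside the Visit 4 row and not replace it.
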